12.1.7. Tables over the whole 24 weeks period

The same tables will be created for the full 24 weeks period of the study, using the 5 groups as specified in section 2.4.

All tables will be created for 3 analysis periods: “first 12 weeks”, “second 12 weeks”, and “full 24 weeks” as defined in section 3.2.

Population: Safety.

Table 14.3.1.16: Treatment-emergent adverse events over the whole study: Summary table

Tabulation per treatment of the number and percentage of subjects with the following:

- Subjects with at least one treatment-emergent adverse event (TEAE)
- Subjects with at least one serious TEAE
- Subjects who died (treatment-emergent)
- Subjects with at least one mild TEAE as worst intensity
- Subjects with at least one moderate TEAE as worst intensity
- Subjects with at least one severe TEAE
- Subjects with at least one TEAE that was considered treatment-related
- Subjects with at least one treatment-emergent SAE that was considered treatment-related
- Subjects with at least one TEAE for which the study treatment was temporarily stopped
- Subjects with at least one TEAE for which the study treatment was permanently stopped
- Subjects with at least one TEAE flagged as an individual stopping criterion by the investigator
- Subjects with at least one TEAE that has not resolved.

Population: safety.

Table 14.3.1.17: Treatment-emergent adverse events over the whole study: Summary table by region

(only for the “full 24 weeks”, not for the two periods separately)

Table 14.3.1.18: Treatment-emergent adverse events over the whole study: Tabulation of all adverse events

Table 14.3.1.19: Treatment-emergent adverse events over the whole study: Tabulation of all adverse events by region

(only for the “full 24 weeks”, not for the two periods separately)

Table 14.3.1.20: Treatment-emergent adverse events over the whole study: Tabulation of all adverse events by gender

(only for the “full 24 weeks”, not for the two periods separately)

Table 14.3.1.21: Treatment-emergent adverse events over the whole study: Tabulation of all adverse events by age category

(only for the “full 24 weeks”, not for the two periods separately)

Table 14.3.1.22: Treatment-emergent adverse events over the whole study: Tabulation per intensity**Table 14.3.1.23: Treatment-emergent adverse events over the whole study: Tabulation of all treatment-related events****Table 14.3.1.24: Treatment-emergent adverse events over the whole study: Tabulation of all treatment-related events by gender**

(only for the “full 24 weeks”, not for the two periods separately)

Table 14.3.1.25: Treatment-emergent adverse events over the whole study: Tabulation of all treatment-related events by age category

(only for the “full 24 weeks”, not for the two periods separately)

Table 14.3.1.26: Treatment-emergent adverse events over the whole study: Tabulation of the intensity of treatment-related events**Table 14.3.1.27: Treatment-emergent adverse events over the whole study: Tabulation of the drug-relatedness of serious events****Table 14.3.1.28: Treatment-emergent adverse events over the whole study: Tabulation of the drug-relatedness of events leading to discontinuation****Table 14.3.1.29: Treatment-emergent adverse events over the whole study: Tabulation of the drug-relatedness of events leading to a temporary stop****Table 14.3.1.30: Treatment-emergent adverse events over the whole study: Tabulation of the drug-relatedness of individual stopping rules****12.1.8. Listings****Listing 16.2.10.1: Treatment-emergent adverse events: Summary listing**

Listing per treatment group, per subject and per analysis period (excluding screening) of the following:

- Period start and end date
- AE preferred term (flagging serious TEAEs with an asterisk *)
- AE start and end date
- AE onset day in study
- AE onset day in period
- AE duration
- AE intensity
- AE drug relatedness
- AE outcome
- AE action taken
- Concomitant therapy started (yes/no)
- Individual stopping criterion (yes/no)

In such a way that all information fits on one line for each AE.

Periods without an AE will be included as “no AE” records.

Population: safety.

Listing 16.2.10.2: Pre-treatment adverse events: Summary listing

Listing per treatment group and per subject of the screening analysis period of all AE details, like in the previous listing. Subjects without an AE can be omitted from this listing.

Population: safety.

Listing 16.2.10.3: Adverse events: Full listing of the serious adverse events

Listing per treatment group, per subject and per analysis period (excluding screening) of all AE details, including MedDRA coding. Only actual serious adverse events will be presented here (irrespective their treatment-emergence, so also showing any SAEs during the screening analysis period).

Population: safety.

Listing 16.2.10.4: Treatment-emergent adverse events: Full listing of the events leading to discontinuation

Same as the previous listing, but only selecting TEAEs that lead to a permanent stop of study medication, or of the study itself. This is including the “stopping rules”.

Population: safety.

Listing 16.2.10.5: Treatment-emergent adverse events: Full listing of the events leading to a temporary stop

Same as the previous listing, but only selecting TEAEs that lead to a temporary stop of study medication.

Population: safety.

Listing 16.2.10.6: Adverse events: Coding information

Listing of all available coding steps between AE verbatim and AE system organ class, mentioning also the subjects who had this AE.

Population: safety.

Listing 16.2.10.7: Adverse events: Listing of subjects for whom a narrative is required

Listing and flagging subjects who:

- Died
- Had an SAE
- Had an AE leading to study discontinuation
- Had an AE leading to a permanent stop of study drug
- Had an AE flagged as stopping criterion by the investigator in the eCRF.

Population: all screened subjects.

The clinical study report will add subject case narratives in the body of the report and/or in section 14.3.1. No standard programming is planned for this.

12.2. LABORATORY SAFETY**12.2.1. Laboratory Units**

The statistical analysis will only present results in Standard International (SI) units. Other units will not be presented.

Lab tests with only a very low sample size ($N < 3$ in the study total column) will not be presented in the tables, but only in the listings. Lab tests that are not part of the planned test panels according to the protocol will only be listed.

Endocrine tests will only be presented for male subjects. If any results would be available for females (not planned in the protocol), then these will be left out of the tables but still presented in the listings.

Urinalysis tests will be presented as part of the descriptive statistics and/or shift tables.

The serum CRP will not be presented in this section (is considered an efficacy parameter).

12.2.2. Derived lab tests

The following two “tests” will be derived from the data provided by the central lab: the ratios TC/HDL and LDL/HDL, where TC=total cholesterol, and the ratio between the CD4 and CD8 absolute counts (CD4/CD8).

Note that if the HDL is zero, the ratios will not be calculated.

The following “normal range” will be applied:

Lab test label in analysis	Normal range, males	Normal range, females
Derived TC/HDL ratio	0.0 - 5.0	0.0 - 4.5
Derived LDL/HDL ratio	0.0 - 3.5	0.0 - 3.0

No normal range is defined for the CD4/CD8 ratio.

These derived “tests” will be analyzed together with the tests provided by the lab.

12.2.3. Number of Significant Digits

The original results and normal limits will be rounded to present only a relevant number of digits. The Mock TLFs contains a table on the expected number of significant digits per lab test. This rounding will be done prior to any parameter derivation. Note that this table also contains the classification of lab tests into categories.

12.2.4. Baseline and Change from Baseline

The baseline is defined as the last sample prior to first dosing, so should normally be from the Day -1 visit. Baseline will be determined per lab test individually. It is recognized that baseline tests may thus come from more than one lab sample and not just from the “baseline visit” sample.

The change from baseline will be calculated for all post-baseline time points as:

Change from baseline at time point t = value at time point t – baseline value.

The percentage change from baseline will be calculated for all post-baseline time points as:

Percent change from baseline at time point t = 100 x (change from baseline at time point t / baseline value).

Note that the percent change from baseline will be left missing in case the baseline value is zero.

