3.3. ALGORITHM OF ALLOCATING VISITS TO TIME WINDOWS

All visits (including early discontinuation visits and unscheduled visits but excluding visits without data) will be placed into time windows according to their relative day (DY) in the study, according to the following allocation table:

Time point label	Target day	Interval lower bound	Interval upper bound
Screening (3)	NA	NA	NA
Baseline (1)	NA	NA	NA
Week 1	8	2	11
Week 2	15	12	21
Week 4	29	22	42
Week 8	57	43	70
Week 12	85	71	98
Week 16	113	99	126
Week 20	141	127	154
Week 24	169	155	182
>Week 24 (2)	NA	183	+∞
Follow-up (3)	7-10 days after last visit	NA	NA

(NA = not applicable).

Notes:

- (1) The actual baseline reference value will be determined per parameter as the last available pre-dosing data point, so might differ from this “baseline” visit interval. There will be only one baseline time point in this study: the last nonmissing value prior to first dosing of study drug.
- (2) Visits falling really late in the study (relative day > 182; excluding the follow-up visit) will be allocated to a “>Week 24” interval, and will not be shown in tables nor figures, but will only be listed.
- (3) For the screening and follow-up visits, no time window is defined. The visit as recorded in the eCRF will be used. Follow-up visits of subjects who discontinue the study prior to the Week 12 re-randomization will be shown separately as well in the tables that present the first part of the study only. For tables that present the study as a whole, all follow-up visits will be shown.

Tables, figures and listings will present the time points, not the visits.

For ECGs, a different method will be used. See section 12.3 for the details.

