Shift table per lab test category (hematology, biochemistry, endocrine, urinalysis), lab test, treatment group and time point. The table will present the shift in abnormality (L/N/...) at worst-case and last on-treatment (other time points: not needed) versus the baseline abnormality (L/N/H). Tests without normal ranges will not be presented in this table.

Population: safety.

Table 14.3.2.5: Laboratory data up to Week 12: Treatment-emergent lab abnormalities per time point

Frequency table of the treatment-emergent lab abnormalities per lab test category (hematology, biochemistry, endocrine, urinalysis), lab test, treatment group and time point (including the worst-case). A post-baseline abnormality is considered treatment-emergent if it differs from the baseline result. Tests without normal ranges will not be presented in this table.

Population: safety.

Table to be created for the Week 12 interim analysis as well.

Table 14.3.2.6: Laboratory data up to Week 12: Frequency table of the CTCAE toxicity grades per time point

Frequency table (with cumulative percentages) per lab test category (hematology, biochemistry, endocrine, urinalysis), lab test, treatment group and time point.

Table for selected tests only.

Population: safety.

Table to be created for the Week 12 interim analysis as well.

Table 14.3.2.7: Laboratory data up to Week 12: Shift table of the CTCAE toxicity grades per time point

Shift table per lab test category (hematology, biochemistry, endocrine, urinalysis), lab test, treatment group and time point. The table will present the shift in CTCAE tox grade (0/1/2/3/4) at worst-case and last on-treatment (other time points: not needed) versus the baseline grade (0/1/2/3/4).

Table for selected tests only.

Population: safety.

Table 14.3.2.8: Laboratory data up to Week 12: Treatment-emergent CTCAE toxicity grades per time point

Frequency table of the treatment-emergent lab CTCAE tox grades per lab test category (hematology, biochemistry), lab test, treatment group and time point (including worst-case). A

post-baseline grade is considered treatment-emergent if it is higher than the baseline tox grade.

Table for selected tests only.

Population: safety.

Table to be created for the Week 12 interim analysis as well.

Table 14.3.2.9: Laboratory data up to Week 12: Frequency table of the ATP III classes per time point

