12.2.11. Tables over the whole 24 weeks period

The same tables will be made as for the first period of the study, but with the 5 adapted treatment groups. Time points to present: screening, baseline, Week 1-2-4-8-12, last on-treatment during period 1, worst case during period 1, Weeks 16-20-24, last on-treatment during period 2, follow-up (all follow-up visits in the study), worst case during period 2, last on-treatment during the whole study, worst case during the whole study. Population: Safety.

Table 14.3.2.14: Laboratory data over the whole study: Descriptive statistics of the actual values per time point

Table 14.3.2.15: Laboratory data over the whole study: Descriptive statistics of the changes from baseline per time point

Table 14.3.2.16: Laboratory data over the whole study: Descriptive statistics of the percent changes from baseline per time point

Table 14.3.2.17: Laboratory data over the whole study: Shift table of the lab abnormalities per time point

Table 14.3.2.18: Laboratory data over the whole study: Treatment-emergent lab abnormalities per time point

Table 14.3.2.19: Laboratory data over the whole study: Frequency table of the CTCAE toxicity grades per time point

Table 14.3.2.20: Laboratory data over the whole study: Shift table of the CTCAE toxicity grades per time point

Table 14.3.2.21: Laboratory data over the whole study: Treatment-emergent CTCAE toxicity grades per time point

Table 14.3.2.22: Laboratory data over the whole study: Frequency table of the ATP III classes per time point

Table 14.3.2.23: Laboratory data over the whole study: Shift table of the ATP III classes per time point

Table 14.3.2.24: Laboratory data over the whole study: Treatment-emergent ATP III classes per time point

Table 14.3.2.25: Laboratory data over the whole study: Frequency table of percent changes from baseline per time point in inhibin B and testosterone

Table 14.3.2.26: Laboratory data over the whole study: Shift table of the categorical lab data per time point

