12.3.3. Baseline and Change from Baseline

The baseline is defined as the last nonmissing value prior to dosing. Baseline will be determined per ECG parameter individually. It is recognized that baseline parameters may thus come from more than one ECG reading and not just from the "baseline visit" reading.

The change from baseline will be calculated for all post-baseline time points as:

Change from baseline at time point t = value at time point t – baseline value.

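### Whole-study laboratory tables judge results after the Week 12 switch to 100 mg only against the pre-first-dose baseline, so carried-over and new abnormalities are counted together

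*SAP*

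**What the plan says.** SAP 3.3 fixes a single reference for the whole study: "There will be only one baseline time point in this study: the last nonmissing value prior to first dosing of study drug". SAP 12.2.4 repeats this for laboratory data: "The baseline is defined as the last sample prior to first dosing, so should normally be from the Day -1 visit". Placebo is study drug, so for the placebo arm this baseline lies before 12 weeks of placebo.

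The flagging rules follow from it. For normal ranges (SAP 12.2.9, Table 14.3.2.5): "A post-baseline abnormality is considered treatment-emergent if it differs from the baseline result". For CTCAE (Table 14.3.2.8): "post-baseline grade is considered treatment-emergent if it is higher than the baseline tox grade".

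SAP 12.2.11 carries these tables over to 24 weeks: "The same tables will be made as for the first period of the study, but with the 5 adapted treatment groups". The groups, listed in SAP 2.1.2, include one for placebo subjects moved to 100 mg and one for 50 mg subjects raised to 100 mg. Besides Weeks 16, 20 and 24, the rows include "last on-treatment during period 2, follow-up (all follow-up visits in the study), worst case during period 2". Under SAP 12.2.8 the period 2 worst case uses values after Week 12 only.

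Adverse events are treated differently. SAP 12.1.1 shows each event only in the period in which it began.

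**The concern.** A period 2 row in the placebo-to-100 mg column invites the reading that its abnormalities appeared on 100 mg. Under the rule some did not: a subject normal at Day -1, high on placebo at Week 12 and still high at Week 16 is flagged in period 2 although nothing emerged after the switch. In the 50-to-100 mg column the same happens with abnormalities that arose on 50 mg. Changes from baseline at Weeks 16 to 24 likewise combine any movement before the switch with movement after it.

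This sits badly with the SAP's own aim in 2.4.1 of charging safety problems to the treatment actually used, and with its onset rule for adverse events. Nothing else fills the gap: SAP 4.5.3 limits the separate second-period safety analysis to adverse events, because laboratory data, ECG and vital signs are left to the whole-study chapter. At stake is whether a reader can tell from the summary tables how many laboratory abnormalities were new after the switch, in up to 70 placebo subjects (Protocol 8.8.2) plus the 50 mg non-responders.

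**Working it through.** The plan states no figure for this, so the check is of the rule itself, followed by illustrations of size.

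**1. The rule applied to patterns** (N normal, H high; SAP reference is Day -1).

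| Day -1 | Week 12 | Period 2 | SAP: emergent in period 2 | Week 12 reference |
|---|---|---|---|---|
| N | N | H | yes | yes |
| N | H | H | yes | no |
| N | H | N | no | no |
| H | N | H | no | yes |
| H | H | H | no | no |

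Row 2 is the carried-over case. Row 3 shows that an abnormality that resolved before the switch does not enter the period 2 rows; it appears in the period 1 and whole-study rows. Row 4 is a missed case. A sixth pattern also matters: normal at Day -1, high at Week 8, normal at Week 12, high in period 2. Both references flag it, so a Week 12 reference alone does not identify everything already seen before the switch.

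**2. Simple counts, assumed rates.** Take n = 70 subjects normal at Day -1 (the full placebo arm, an upper bound). Let q be the proportion abnormal at Week 12, r the proportion of those still abnormal later, and t the proportion newly abnormal on 100 mg among those normal at Week 12. None of these is in the documents.

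- SAP period 2 count = n[qr + (1 − q)t]
- Week 12 reference count = n(1 − q)t

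With q = 10%, r = 50%, t = 5%: 70 × (0.05 + 0.045) = 6.7 against 70 × 0.045 = 3.2. The carried-over share is 3.5/6.65 = 53%. Over q 5–20%, r 25–75%, t 5–10% the counts run from 4.2 to 16.1 (SAP) and from 2.8 to 6.7 (Week 12). With r allowed to run from 0 to 100%, the carried-over share runs from 0% (nothing persists) to 14/16.8 = 83%.

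**3. Model with visit-to-visit noise and no drug effect.** Assumed: standardised value = subject mean (variance 0.7) + drift d + visit noise (variance 0.3); no drift at Day -1 and full drift at every later visit; five visits in period 1 and three in period 2; high if above U. With F_d(s) = Φ((U − s − d)/√0.3) and E the average over subject means s:

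- SAP rate = E[F_0(1 − F_d³)]
- Week 12 rate = E[F_d(1 − F_d³)]
- Share of SAP cases high at Week 12 = E[F_0(1 − F_d)(1 − F_d³)] / SAP rate
- Share high at any period 1 visit = 1 − E[F_0·F_d⁵(1 − F_d³)] / SAP rate

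| U (SD) | d (SD) | SAP rate | Week 12 rate | High at any period 1 visit | High at Week 12 |
|---|---|---|---|---|---|
| 1 | 0 | 15.8% | 15.8% | 69% | 30% |
| 1 | 0.3 | 25.8% | 19.8% | 77% | 38% |
| 1 | 0.6 | 37.5% | 22.5% | 84% | 47% |
| 1.5 | 0 | 8.8% | 8.8% | 60% | 24% |
| 1.5 | 0.3 | 15.9% | 12.9% | 69% | 31% |
| 1.5 | 0.6 | 25.7% | 17.2% | 77% | 39% |
| 2 | 0 | 3.7% | 3.7% | 52% | 19% |
| 2 | 0.3 | 7.6% | 6.4% | 61% | 25% |
| 2 | 0.6 | 13.8% | 10.1% | 69% | 31% |

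At d = 0 the two rates must be equal, because F_0 = F_d. With drift the SAP rate is higher by 1 to 15 percentage points. If drift builds up linearly over the 12 weeks, the rates are unchanged and the share high at any period 1 visit becomes 50% to 69%.

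**The case against.** The strongest reply is that the SAP never attributes these counts to 100 mg. The columns are labelled as treatment sequences, period 1 rows stand beside period 2 rows, the tables carry no p-values (12.2.9), and one fixed baseline keeps the five groups comparable. Timing is recoverable: Figure 14.3.2.4 plots the profile of each subject with a treatment-emergent abnormality, and Listing 16.2.11.2 gives every out-of-range value with its baseline reference. Mean change since Week 12 is, dropouts aside, the difference between two displayed rows; only its standard error is missing. All of this stands, and it is why the common baseline should stay. What remains is that adjacent percentages in a table cannot show how many period 2 cases were already abnormal before the switch.

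Four stronger readings are tempting, and the documents or the check do not support them.

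- *ECG and vital signs have the same defect.* Their baselines are also pre-dose (for ECG, "The baseline is defined as the last nonmissing value prior to dosing"), but SAP 12.3.7 and 12.4.7 describe the whole-study groups as centred on subjects who took GLPG0634 in both periods. Read literally, this leaves out the placebo switchers and conflicts with 2.1.2. For them the point cannot be asserted until the sections are reconciled.
- *Every abnormality that arises on placebo is charged to period 2.* Only those present after Week 12 are.
- *The 3.7% to 37.5% is inflation caused by the baseline.* Much of it is visit noise and repeated looks; the excess over a Week 12 reference is 0 to 15 points.
- *The rule is at least conservative.* Row 4 of the pattern table shows that it can miss a case.

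**Conclusion.** The point holds for the laboratory whole-study tables that compare with baseline: 14.3.2.15–18, 14.3.2.20–21 and 14.3.2.23–26. Table 14.3.2.19 is a frequency of grades with no baseline comparison and is not affected. For both switcher groups, period 2 treatment-emergent counts mix carried-over with new abnormalities, and no planned summary separates them.

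The size cannot be fixed from the documents. Under the assumptions in step 3, between half and 84% of the flagged cases had been abnormal at some period 1 visit, and 19% to 47% were abnormal at Week 12 itself. How far the choice of reference moves the total depends on drift before the switch: not at all without drift, by up to 15 points at 0.6 SD. This is a weakness in how descriptive safety results can be read. It does not touch the primary endpoint or the placebo-controlled period 1 safety tables.

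**What to change.** Keep the Day -1 baseline as the main display for all five groups. For the placebo-to-100 mg and 50-to-100 mg columns, add to the laboratory tables:

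- period 2 rows for change and for treatment-emergent abnormality against the last value before the first post-switch dose, normally Week 12;
- a split of period 2 worst-case abnormalities into already seen in period 1 and new in period 2, showing both.

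Both are needed, since a Week 12 reference alone leaves earlier period 1 abnormalities among the new cases. Neither part of the split should be dropped. In the step 3 model with zero drift, U = 1 SD and a true drug effect of 0.5 SD, counting only subjects with no abnormality at Day -1 or in period 1 would cut the flagged rate from 33.4% to about 16%.

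Reconcile SAP 12.3.7 and 12.4.7 with 2.1.2 on whether placebo switchers are in the whole-study ECG and vital-sign tables. If they are, add the same pre-switch reference there; SAP 12.3.4 provides no worst-case row for ECG, so the split would not apply to it.

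The cost is SAP wording, one derived flag and slightly longer tables. No new data are needed: laboratory tests and vital signs are taken at every visit, and an ECG is taken at Week 12.
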